3.5.2 OUTCOMES DEFINITIONS

Myocardial Infarction (MI): Defined as the death of part of the myocardium due to an occlusion of a coronary artery from any cause, including spasm, embolus, thrombus or rupture of a plaque. MACH15 will use standard case definitions for both fatal and nonfatal MI based on the combination of symptoms, elevation in biomarkers, and/or ECG findings. The algorithm for classifying MI includes elements of the clinical presentation (signs and symptoms), results of cardiac biomarker determinations, and ECG readings, and is based on the 2003 American Heart Association Position Statement “Case Definitions for Acute Coronary Heart Disease in Epidemiology and Clinical Research Studies”² and consideration of the 2012 “Third Universal Definition of Myocardial Infarction”.³ MACH15 adjudicators will be guided by specific, pre-specified definitions and operational rules. Adjudicators will use their clinical interpretation of the ECGs and other available evidence for the event to classify the MI.²

Stroke: MACH15 will use standard case definitions for both fatal and nonfatal stroke. Stroke will be defined based on all available data, including symptoms and signs, imaging of the brain and large vessels, and cardiac testing, e.g., echocardiography. Based on “An Updated Definition of Stroke for the 21st Century” AHA/ASA Expert Consensus Document,⁴ central nervous system (CNS) infarction will be defined as A) pathological, imaging, or other objective evidence of CNS injury in a defined vascular distribution; or B) clinical evidence of CNS injury based on symptoms persisting ≥ 24 hours or until death, and other etiologies excluded. Exclusionary conditions for stroke include major brain trauma, intracranial neoplasm, coma due to metabolic disorders or disorders of fluid or electrolyte balance, peripheral neuropathy, or central nervous system infections. In cases where there is enough documentation, stroke will be classified by subtype.

Hospitalization for angina (or non-MI acute coronary syndrome) is defined as overnight hospitalization for symptoms, such as chest pain, chest tightness, or shortness of breath, produced by myocardial ischemia that do not result in myocardial infarction, but are treated medically or surgically during an overnight stay. The symptoms generally last less than 20 minutes, and may have occurred prior to the admission. This definition also includes hospitalizations for the diagnosis of angina/symptomatic coronary artery disease from a physician based on history and a positive diagnostic test (angiography, exercise stress testing, perfusion scan or stress echocardiogram).

Coronary/carotid revascularization: Revascularization is confirmed when participants undergo urgent or elective coronary bypass grafting, angioplasty, endarterectomy, thrombectomy, or any similar procedure intended primarily to ameliorate coronary/carotid artery stenoses.

Death attributable to cardiovascular disease (CVD): death attributable to CVD events, defined as those that comprise the MACH15 primary outcome (specifically MI, ischemic stroke, hospitalized angina, and coronary/carotid revascularization), and based on temporal relationship considering event medical records (e.g., hospitalization for MI or stroke), or postmortem findings related to an acute CVD event.

Other: In addition to the above, MACH15 will assess additional diabetes related outcomes:

- Progression among normoglycemic and pre-diabetes individuals to ADA-defined diabetes;
- Progression among normoglycemic individuals to ADA-defined prediabetes.

Both these ADA-defined outcomes will be confirmed by two measurements of either HbA1c or fasting plasma glucose obtained at the annual clinic visits or based on documented use of medication treated diabetes starting between in-person clinic visits.

4 PARTICIPANT ENROLLMENT

4.1 INCLUSION/EXCLUSION OVERVIEW

The objective of identifying formal inclusion/exclusion criteria is to enroll a trial population that will ensure adequate event rates for statistical power, promote generalizability, and maximize safety. Inclusion/exclusion criteria have been made as simple as possible to ensure standard implementation across all clinical sites. Specifically, the eligibility criteria have been developed to facilitate the identification and inclusion of a trial population that will adhere to the trial protocol and are at above average risk for cardiovascular disease.

Implementation of these inclusion/exclusion criteria and related recruitment strategies will be accomplished to meet several goals with respect to the composition of the trial population. The overall goal for recruitment is approximately 7,800 participants to include ~50% women and demographic characteristics representative of the community surrounding each of the MACH15 clinical sites. In recruitment, there is an implicit hierarchy based on trial hypotheses and design considerations: first, attain the overall sample size for sufficient power to test the main hypothesis of trial; and second, ensure a sufficiently diverse trial population so that results are broadly applicable. Recruitment of a cohort of participants that are committed to helping answer the scientific question by adherence to their protocol assigned treatment is essential as non-adherent participants, drop-outs and suspected losses to follow-up will not be replaced with newly recruited participants.

These goals will be monitored on an ongoing basis and the Recruitment and Retention Subcommittee (R&R) and the Steering Committee will evaluate recruitment strategies and implement corrective actions as needed (see Manual of Procedures [MOP] for specific strategies and actions).

4.2 PARTICIPANT INCLUSION CRITERIA

To be eligible for the MACH15 Trial an individual must meet all of the following criteria:

1. Age ≥ 50 years at screening
2. Postmenopausal, defined as 12 consecutive months without menstruation
3. Not alcohol naïve, defined by having consumed at least one drink of alcohol in the past five years
4. High risk for the occurrence of a new cardiovascular disease event, defined as having any one of the following:
 - a) American Heart Association (AHA)/American College of Cardiology (ACC) Risk Score $\geq 15\%$ within the past 24 months (among those without clinical or subclinical cardiovascular disease [CVD])
 - b) Clinical CVD (more than 6 months prior to randomization), defined by:
 - 1) Previous myocardial infarction (MI), percutaneous coronary intervention (PCI), coronary artery bypass grafting (CABG), carotid endarterectomy (CE), carotid stenting;
 - 2) Peripheral artery disease (PAD) with revascularization;

- 3) Acute coronary syndrome with or without resting electrocardiogram (ECG) change, ECG changes on a graded exercise test (GXT), or positive cardiac imaging study;
- 4) Prior stroke documented on brain imaging or with a persistent deficit.
- c) Subclinical CVD, confirmed in available medical records:
 - 1) At least a 50% diameter stenosis of a coronary, carotid, or lower extremity artery;
 - 2) Coronary artery calcium score ≥ 400 Agatston units;
 - 3) Ankle brachial index (ABI) ≤ 0.90 ;
 - 4) Left ventricular hypertrophy (LVH) by ECG (based on computer reading), echocardiogram report, or other cardiac imaging procedure report;
 - 5) Abdominal aortic aneurysm (AAA) ≥ 5 cm with or without repair.
- d) Age ≥ 75 years

Note that eligible individuals residing in the same household can participate if they agree to be randomized as a unit to the same intervention at the same randomization time.

4.3 PARTICIPANT EXCLUSION CRITERIA

An individual who has any of the following criteria will be excluded from participation in MACH15 (see MOP for further detail regarding criteria and/or assessment tools):

1. High alcohol consumption, defined by any one of the following:
 - a) Alcohol Use Disorders Identification Test (AUDIT) score > 5 at screening
 - b) Drinking, on average, > 7 alcoholic beverages/week during the past 6 months
 - c) Drinking 6 or more alcoholic beverages on one occasion during the past 6 months.
2. Yale-Brown Obsessive Compulsive Scale-heavy drinking (Y-BOCS-hd) total score of ≥ 6 on questions 7, 8, and 10
3. Within the 6 months prior to randomization, cardiovascular disease event (MI, revascularization procedure, or stroke)
4. AHA Class III-IV heart failure
5. History of alcohol or substance abuse (medical record confirmed or self-reported history)
6. Other intolerance or allergy to alcohol
7. Dual antiplatelet therapy or coumarin anticoagulants
8. History of gastric bypass surgery
9. Any serious chronic liver disease (e.g., active hepatitis B and C infections) or liver tests (aspartate aminotransferase [AST], alanine aminotransferase [ALT] and gamma-glutamyl transpeptidase [GGT]) > 2 times the upper limit of the normal range using local standards
10. Personal history of any colon or liver cancer

11. Any other cancer with a life expectancy of less than 3 years
12. Diagnosed with breast cancer that required either surgery or removal of breast tissue or chemotherapy
13. Mother or sister ever diagnosed with breast cancer that required either surgery or removal of breast tissue or chemotherapy
14. Estimated glomerular filtration rate (eGFR) <30 ml/min /1.73m² or end-stage renal disease (ESRD)
15. Ongoing use of any medication for which alcohol consumption is contraindicated
16. A Patient Health Questionnaire (PHQ-9) ≥15 at screening or a positive response on question 9 dealing with suicide ideation
17. History of any organ transplant
18. Unintentional weight loss >10% in last 6 months
19. Currently participating in another clinical trial (intervention trial) with CVD outcomes. Note: Participant must wait until the completion of his/her activities or the completion of the other trial before being screened for MACH15. Local restrictions for entry by participants can be more conservative if mandated.
20. Not willing or able to provide a name and contact information for at least one additional contact person other than self
21. Diagnosis of dementia
22. Investigator discretion regarding appropriateness of participation or concern about intervention adherence, examples include: moderate – severe psychiatric illness, behavioral concerns regarding likelihood of low adherence to trial protocol, a medical condition likely to limit survival to less than 3 years, or an advanced chronic disease, such as cognitive impairment without a dementia diagnosis or any condition that requires 24-hour care.
23. Not willing or able to provide a signed and dated informed consent form
24. Unable to successfully complete the washout period
25. Not willing or able to comply with all trial procedures

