7.4.4 REPORTING OF PREGNANCY

The use of alcohol is a known risk factor during pregnancy. One of the main inclusion criteria in the trial is postmenopausal status. Therefore, women included in the trial will have a postmenopausal status and pregnancies are not expected to occur. However, if a pregnancy does occur, participation will be discontinued on the intervention.

7.4.5 INCIDENT CONDITIONS THAT RESULT IN PERMANENT OR TEMPORARY STOPPING OF ALCOHOL BUT CONTINUED FOLLOW-UP FOR OUTCOMES

The use of alcohol may be harmful in the following conditions. For this reason, the intervention will be discontinued at least temporarily in the following incident conditions (this list is not intended to be exhaustive):

- Dementia
- Heart failure Class III or IV
- Breast cancer
- Gastric bypass surgery
- Serious chronic liver disease (e.g., active hepatitis B and C infections) or liver tests (aspartate aminotransferase [AST], alanine aminotransferase [ALT] and gamma-glutamyl transpeptidase [GGT]) >2 times the upper limit of the normal range using local standards; GI bleeding.
- Estimated glomerular filtration rate (eGFR) drops to <30 ml/min /1.73m² or end-stage renal disease (ESRD)
- Ongoing use of any medication for which alcohol consumption is contraindicated
- A Patient Health Questionnaire (PHQ-9) score ≥15 or a positive response on question 9 dealing with suicide ideation
- Any organ transplant
- Pregnancy
- Development of alcohol use disorder

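### GI bleeding stops alcohol after randomization (7.4.5), but no entry criterion in 4.2 or 4.3 covers an active or recent bleed

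*Combined protocol and SAP*

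**What the plan says.** Section 7.4.5 gives its reason first: "The use of alcohol may be harmful in the following conditions". It then sets the action: "the intervention will be discontinued at least temporarily in the following incident conditions". The list has 11 bullets. The liver bullet ends ">2 times the upper limit of the normal range using local standards; GI bleeding", so GI bleeding shares a line with liver disease and liver tests, separated by a semicolon.

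On the entry side, exclusion 9 in section 4.3 opens "Any serious chronic liver disease (e.g., active hepatitis B and C infections) or liver tests" and sets the same threshold of twice the upper limit of normal. It stops there, without GI bleeding. None of the 4 inclusion criteria in 4.2 or the 25 exclusions in 4.3 mentions GI bleeding, ulcer or a bleeding history.

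The general route to exclusion is number 22: "Investigator discretion regarding appropriateness of participation or concern about intervention adherence". Its examples are open-ended and do not name bleeding. Section 4.1 states the aim of the criteria: "Inclusion/exclusion criteria have been made as simple as possible to ensure standard implementation across all clinical sites".

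The only other mention of GI bleeding is in section 1.1, among the outcomes of excessive drinking.

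**The concern.** The protocol treats the same event differently on either side of randomization. A participant who bleeds the day after randomization to alcohol must stop, at least for a time. A person who bled shortly before randomization meets no named exclusion and, if assigned to alcohol, starts a daily drink. The documents do not explain the difference.

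What is at stake is patient safety and uniform practice. Whether a recent bleed keeps someone out depends on individual judgment at 16 to 20 sites (section 4.4.1), which works against the standard implementation that 4.1 asks for. Later safety reporting does not fill the gap. A bleed that is life-threatening or leads to hospital admission is captured as an SAE (7.1.2, 7.4), but only after exposure. GI bleeding is not among the events of special interest in 7.4.3, so under 7.1 a non-serious bleed is not systematically collected unless it leads to trial discontinuation.

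**Working it through.** The plan has no figure to reproduce on this point. The check is a comparison of texts, followed by arithmetic for scale.

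**Step 1. Match each 7.4.5 condition to the entry criteria.** Counting GI bleeding apart from the liver conditions turns 11 bullets into 12 conditions.

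| 7.4.5 condition | Entry counterpart | Match |
|---|---|---|
| Dementia | Exclusion 21 | Direct |
| Heart failure, Class III or IV | Exclusion 4 | Direct |
| Gastric bypass | Exclusion 8 | Direct |
| Liver disease or raised liver tests | Exclusion 9 | Direct |
| eGFR below 30, or ESRD | Exclusion 14 | Direct |
| Medication contraindicating alcohol | Exclusion 15 | Direct |
| PHQ-9 of 15 or more, or positive question 9 | Exclusion 16 | Direct |
| Organ transplant | Exclusion 17 | Direct |
| Breast cancer | Exclusion 12, limited by the treatment required | Partial |
| Pregnancy | Inclusion 2, postmenopausal status | Indirect |
| Alcohol use disorder | Exclusion 5, with 1 and 2 | Partial |
| GI bleeding | None | None |

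The count is 8 + 3 + 1 = 12. Splitting liver disease from liver tests, eGFR from ESRD, and the PHQ-9 score from question 9 gives 12 + 3 = 15 items. GI bleeding is still the only one unmatched.

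**Step 2. Look for another rule that would catch a bleed.**
- Exclusion 7 covers dual antiplatelet therapy and coumarins, which are drugs rather than the event.
- Exclusions 9, 10 and 15 cover liver disease, colon or liver cancer, and medications. They remove some people who have also bled, but none depends on the bleed.
- Screening takes a medical history to determine eligibility (6.1.1.4). Eligibility is checked again at the washout call (6.3.4) and on the day of randomization (6.3.5). An active bleed would probably be noticed at one of these contacts, although none names bleeding.
- Exclusion 22 permits exclusion but does not require it for a bleed.

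The realistic gap is therefore a recent bleed that has resolved by the time of screening.

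**Step 3. Scale.** The documents give no frequency of recent bleeds. I assume 0.1% to 1% of recruits, for illustration only, and that exclusion 22 is never used.
- Entrants: 0.001 × 7,800 = 7.8 and 0.01 × 7,800 = 78.
- Assigned alcohol under the balanced design (3.1): 7.8 / 2 = 3.9 and 78 / 2 = 39.

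**Step 4. Recruitment cost of a rule.** Section 8.3 expects 11 participants per site per month.
- Trial-wide monthly rate: 11 × 16 = 176 to 11 × 20 = 220.
- Time to replace those excluded: 7.8 / 220 = 0.035 month to 78 / 176 = 0.44 month.

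**The case against.** The strongest reply is that 7.4.5 does not reach the case in question. It governs incident conditions, allows a temporary stop with no minimum length, and does not say that alcohol is harmful once a bleed has resolved. Where it speaks clearly (active bleeding), screening would probably catch the person. Where the gap lies (a resolved bleed), it is silent. This narrows the point but does not remove it. A stop triggered by a bleed runs for some time after the event, and with scheduled contacts mostly three months apart, sites will often learn of a bleed only afterwards. In practice the stopping rule acts on recent bleeds.

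Other objections carry some weight:
- The 7.4.5 list is not meant to be exhaustive, and the two lists were not designed as mirrors. That is true, and the count alone proves no error. But GI bleeding is a condition the sponsor chose to name.
- The semicolon could tie GI bleeding to liver disease, which exclusion 9 would then cover. That reading is possible but strained.
- Section 1.1 links GI bleeding to excessive drinking, and 1.4.1 does not list it as a risk of moderate intake. This stands. The point rests only on the possible harm stated in 7.4.5.
- The Manual of Procedures may help, but it is not in the documents, and 4.3 describes it as giving further detail on the criteria and assessment tools.
- A discretion clause fits the wish for simple criteria. It fits the wish for standard implementation less well.

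**Conclusion.** The concern holds and should be fixed. GI bleeding is the only condition in 7.4.5 with no counterpart at entry, so exclusion after a recent bleed is optional rather than required. The textual finding is firm. Its practical size is not known from the documents: the figure of about 4 to 39 people assigned alcohol rests on an assumed frequency of 0.1% to 1% and on exclusion 22 never being used. I make no estimate of excess bleeding risk at the trial dose and claim no effect on power or on the contrast between arms. Because 7.4.5 allows a temporary stop, it supports a time-limited exclusion and not a bar for any past bleed.

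**What to change.** Add to 4.3 an exclusion for active GI bleeding or GI bleeding within a set window before randomization. The medical leads should set the window. Six months, as exclusion 3 uses for cardiovascular events, is a convenient precedent, but the documents give no gastrointestinal rationale for it. Ask about bleeding in the screening medical history, and allow re-screening under 4.4.5 once the window has passed.

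The cost is one exclusion line, one question in a history already taken, and a small loss or delay of recruits. Under the assumed 0.1% to 1% that is 8 to 78 people, or about 0.04 to 0.44 month of recruitment, some of it recovered through re-screening.

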4.4 STRATEGIES FOR RECRUITMENT

4.4.1 RECRUITMENT OVERVIEW

The recruitment goal of MACH15 is to enroll approximately 7,800 participants, approximately 500 at each of the 16-20 clinical sites around the globe, who have an above-average cardiovascular risk.

Participants will be recruited over a 3-year period and followed for an average of 6 years. Due to the international nature of the trial, clinic-specific minority enrollment targets will be determined.

All recruitment related activities will be overseen by the Recruitment & Retention (R&R) Subcommittee. To accommodate the variability across global regions in catchment area characteristics, media market outlets, and access to eligible participants, each clinical site will develop and submit to R&R a clinical site-specific recruitment plan. All recruitment materials will be reviewed and approved by the appropriate clinical site Institutional Review Board/Ethics Committee (IRB/EC) before being used.

The R&R Subcommittee will play a significant role in monitoring the progress of trial-wide recruitment and provide a forum for advising clinical sites on problem identification, goal-setting, strategy deployment and evaluation in their efforts to achieve site and trial-wide recruitment goals. In addition, the R&R Subcommittee will collate and evaluate recruitment strategies during the vanguard phase and advise all clinical sites on their effectiveness to maximize trial-wide recruitment.

4.4.2 RECRUITMENT ACTIVITIES

A multifaceted approach to screening and enrollment is essential to achieve the recruitment goal. For this global multicenter trial, recruitment strategies targeting both existing populations within the clinical practice of the clinical sites as well as individuals from outside these practice settings will be used to identify potentially eligible participants.

Recruitment for the trial will utilize specific community resources to promote recruitment of women and minority/under-served populations to ensure adequate representation of groups residing in the communities surrounding the clinical sites. Recruitment strategies that have worked well in other trials related to cardiovascular disease^{1,2} will be employed. Sites may focus on:

- 1) Recruitment from within a general practice or other medical practice or health system–based setting; and/or
- 2) Community-based recruitment.

4.4.3 RECRUITMENT IN EXISTING POPULATIONS IN CLINICAL SITES EMBEDDED WITHIN MEDICAL PRACTICES/HEALTH SYSTEMS

Methods for identifying potentially eligible participants within the clinical practice or the research clinic settings may include: a targeted review of medical records or databases for those meeting the trial's inclusion criteria, referrals from providers/employees within the practice, and/or from practice participants themselves. Additional approaches may also include written materials developed centrally and/or locally such as direct mailing and/or availability of trial brochures and posters in the medical offices. Locally developed materials are encouraged in collaboration with the local IRB/EC and the Coordinating Centers (see MOP).

4.4.4 SCREENING

To minimize in-person screening visits by ineligible volunteers, persons demonstrating interest in the trial may complete a phone or on-line pre-screening as allowed by the local IRB/EC. Potential trial

participants may also attend a pre-screening visit for the same purpose. Potential participants must attend the Screening Visit to complete all necessary screening assessments (see *Chapter 6: Trial Procedures and Schedules*). According to local IRB/EC regulations, informed consent will be obtained for screening and possible trial participation as well as data sharing, potential genetic studies, and sample storage. No data will be collected prior to informed consent.

4.4.5 RE-SCREENING OF PARTICIPANTS PREVIOUSLY NOT MEETING INCLUSION/ EXCLUSION CRITERIA

Under certain circumstances participants that failed to meet certain eligibility criteria or met certain exclusion criteria initially (temporarily on dual antiplatelet therapy, CVD event less than 6 months, etc.) may be re-screened (see MOP for process).

